Problems/weaknesses: The very nature of this study in regard to inclusion criteria, namely negative standard or extensive clinically diagnostic imaging scans, is problematic in determining "truth" regarding whether or not a foci of 99mTc sestamibi is secondary to metastatic DTC. But that problem should not stop one from performing such a study evaluation for these problematic patients.

Risk/Benefit Assessment: The risk/benefit assessment for this study is very low. The risk of side effects is typically <1%, and if they occur they are minor. The likelihood of benefit is not known and is the objective of the study; however, if the source of the patient's elevated serum thyroglobulin is identified, this could have significant potential benefit because of the potential for earlier treatment and avoidance of complications from the site of metastases later.

Study Population-Gender/Ethnic Inclusion: The selection of the study population is not based on gender or ethnicity.

Data Management: As noted above, confidentiality will be maintained by coding each patient, and all of the patient's identifiers will be stored on the principal investigator's computer in which the file and the computer are password protected.

Subject Identification: All patients will be identified in the Division Nuclear Medicine at the MedStar Washington Hospital Center.

Participation of Children: Children of less than 18 years of age are not eligible to participate in this clinical trial.

Compensation Plan for Subjects: None

Informed Consent: Attached

Vertebrate Animals: Not applicable

Consultants—None

Budget:

The work will be performed by [name] ([name]) and [name] (CL) and subsequently [name] (DW), future research assistant, who will be added to the study on arrival. [name] works without salary or compensation and CL's and DW's salary will be paid from the research fund for thyroid cancer research.

For expenses related to abstract submission, poster presentation, travel for presentations, etc. will be paid from the research fund for nuclear medicine thyroid cancer.

For the ^{99m}Tc Sestamibi radioisotope and scan, per [name], the expense is \$295.94 for the 78801 scan code, which includes ^{99m}Tc tetrafosmin. Because we will be using ^{99m}Tc sestamibi, there is an additional \$10.00 surcharge.

Item	Charge	Units	Subtotal
78801 scan	\$295.94	15	\$4439.10
Surcharge for ^{99m} Tc Sestamibi	\$10	15	\$150.00
Poster preparation, travel, lodging for	\$1900	1	\$1900

Presentation of initial results

Poster preparation, travel, lodging for Presentation of final results	\$1900	1	\$1900
--	---------------	----------	---------------

Manuscript preparation and submission including journal fees, etc.	\$1800	1	\$1800
---	---------------	----------	---------------

Statistical analysis and support	\$1500	1	\$1500
---	---------------	----------	---------------

Miscellaneous expenses			\$1200
-------------------------------	--	--	---------------

[name]			Salary already covered
-----------------------	--	--	-------------------------------

[name]			Salary already covered
--------------	--	--	-------------------------------

[name]			Pro bono
-----------------------	--	--	-----------------

Appendices

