Adverse event reporting requirements to the MHRI Institutional Review Board (IRB) for this

protocol are as follows:

- Investigators will submit a completed serious adverse event report to the MRI IRB within 7 days after becoming aware of a subject death, a potentially life-threatening (grade 4) serious adverse event that is possibly, probably or definitely related to investigational agent, an inpatient hospitalization (other than elective or the I-131 treatment), a persistent or significant disability/incapacity, or a congenital anomaly/birth defect.
- Investigators will submit a completed serious adverse event report to the MHRI IRB within 15 days after becoming aware of any Grade 3 (severe) adverse event that is possibly, probably or definitely related to investigational agent.
- Investigators will report within 15 days on any other event or condition regardless of grade, which in their judgment represents an event reportable to the IRB.
- A summary of all adverse events will be reported to the MHRI IRB with submission of a request for continuing review.

Interpretation of ^{99m}Tc Sestamibi Study.

- A. A team of two nuclear medicine physicians will interpret the ^{99m}Tc sestamibi, and any area of radioactivity will be graded as by a standard nuclear medicine grading system:
1. Normal physiological activity
 2. Probably physiological activity
 3. Indeterminate activity
 4. Probably metastatic disease
 5. Metastatic disease
- B. Criteria for “final determination” regarding whether a finding represents physiological activity or metastatic disease:
- a. For findings graded as 1 or 2, they will be defined for this study as physiological activity.
 - b. For findings graded as 3, or 4, the following will be required:
 - i. **Biopsy**; however, this will only be performed if clinically indicated.

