 1. **Follow-up**: It is anticipated that very few biopsies will be performed and because the criteria for entering this study is NDCIS or NECIS, the only alternative for confirming whether or not a foci of ^{99m}Tc sestamibi uptake on a scan is metastases will be follow up, which will be performed on a clinical bases depending on the patient’s treating physicians’ decisions. The study team will follow up through telephone at 1, 3, 6 and 12 months after the sestamibi scan and/or until diagnosis of the metastatic site. The purpose of the telephone follow-up is to enquire on what, if any, blood tests, imaging studies or biopsies were ordered by the patient’s treating physician. However, if on follow up any of the following occur, then the focus will be categorized as a metastases (true positive).
 - a. Subsequent biopsy,

- b. Subsequent clinical imaging study(s) (For example, although a lytic bone lesion in the area of interested was not present initially on the CT, a lytic lesion indicative of metastases may subsequently develop in that area, and for this study this will be defined as evidence of metastases of DTC (true positive).
- ii. **Blind I-131 treatment**** with or without a prefatory scan: If a “blind” I-131 treatment” is clinically selected and the post I-131 therapy scan demonstrates uptake in the same areas as the ^{99m}Tc sestamibi, then the finding on the ^{99m}Tc sestamibi will be classified for this study as a metastases of DTC.
- c. Grade 5 is not anticipated, because unlike I-131, which can have patterns that are very specific for DTC, ^{99m}Tc sestamibi patterns are not specific for DTC.

** A “blind I-131 treatment” is a potential therapeutic option, and this term means that the treating physician or team cannot identify the source of the patient’s elevated Tg, but because of factors such as the level of elevated Tg, the rate of rise of the Tg, and the patient’s clinical situation, a therapeutic administration of I-131 is give despite being “blind” to the source of the Tg.

Patient Numbers

[figure not shown]
- a. As noted in the objective of this study, this is a pilot study. As a pilot study, the present plan is to perform 15 patients. If no findings of Grade 3, 4, or 5 are identified on the first fifteen ^{99m}Tc sestamibi scans, then the study will be terminated.

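### Every written criterion for a Grade 3 or 4 focus leads to metastasis: the biopsy criterion states no result, and nothing says when a focus counts as refuted or unresolved

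*Protocol*

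**What the plan says.** Part B of the protocol section Interpretation of 99mTc Sestamibi Study gives criteria for a final determination "regarding whether a finding represents physiological activity or metastatic disease". It works by grade.

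- **Grades 1 and 2.** The initial reading settles the matter: "For findings graded as 1 or 2, they will be defined for this study as physiological activity".
- **Grades 3 and 4.** Biopsy is done only where clinically indicated, and "It is anticipated that very few biopsies will be performed". Otherwise the focus is judged on follow-up under routine care. The team telephones at 1, 3, 6 and 12 months "after the sestamibi scan and/or until diagnosis of the metastatic site", and the purpose of the calls is "to enquire on what, if any, blood tests, imaging studies or biopsies were ordered". The rule then reads: "However, if on follow up any of the following occur, then the focus will be categorized as a metastases (true positive"). Two events are listed. One is "Subsequent biopsy", with nothing about its result or site. The other is later clinical imaging, illustrated by a new lytic bone lesion in the area of interest. Separately, after a blind I-131 treatment, a focus is classed as metastasis if "the post I-131 therapy scan demonstrates uptake in the same areas as the" sestamibi scan.
- **Grade 5.** Not anticipated, and given no rule.

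Patient Numbers, item b, says that patients with Grade 3 to 5 findings are followed to establish, as far as reasonably possible, whether those findings are metastatic or not. No further patients are recruited until those data have been reviewed. The paragraph Problems/weaknesses concedes that truth is hard to establish in patients selected for negative imaging.

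**The concern.** Part B announces a two-way determination, but its criteria for the foci that need one point in a single direction. Two consequences follow.

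First, the biopsy criterion is met by the occurrence of a biopsy. Applied to the letter, a benign biopsy of the focus makes it a true positive.

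Second, a focus shown to be benign and a focus that nobody worked up end in the same place, namely outside any stated class. They carry different information: one is evidence against the scan finding, the other is no evidence. The second kind may be common, because few biopsies are expected and further tests are left to the treating physicians.

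The classified foci are the data that Patient Numbers, item b, sends to review before recruitment can resume. Without classes, whoever reviews them must decide case by case whether a focus with no label is physiological, excluded or still pending.

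**Working it through.** The protocol gives no figure to reproduce here, so the main check sets each possible event for a Grade 3 or 4 focus against the class that Part B assigns.

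| Event after the scan | Class under Part B |
|---|---|
| Biopsy positive for differentiated thyroid cancer (DTC) at the site | Metastasis |
| Benign biopsy of the site | Metastasis if read literally; otherwise none stated |
| Later imaging indicating metastasis at the site | Metastasis |
| Later imaging showing a benign explanation at the site | None stated |
| Later imaging negative | None stated |
| Post-therapy I-131 uptake in the same area | Metastasis |
| Post-therapy I-131 scan not matching | None stated |
| No work-up by the 12-month call | None stated |

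All three written criteria (biopsy, imaging, matching post-therapy uptake) lead to metastasis; none leads to physiological activity or to an unresolved class. The open-ended limb of the follow-up period also closes only on a metastatic diagnosis.

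**Illustration of size.** Only N = 15 comes from the protocol (Patient Numbers, item a). The rest is assumed: one focus per patient, 6 patients with a Grade 3 or 4 focus, of which 2 confirmed, 1 refuted and 3 unresolved. Intervals are exact 95% (Clopper-Pearson): lower limit = Beta quantile 0.025 with parameters (x, n − x + 1); upper limit = Beta quantile 0.975 with parameters (x + 1, n − x).

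1. Confirmed yield, with biopsy read as positive biopsy: 2/15 = 13% (2% to 40%) of scanned patients and 2/6 = 33% (4% to 78%) of those with a focus. This is the same with or without the extra classes.
2. Upper bound with unresolved foci counted as confirmed. As written, the 6 − 2 = 4 unconfirmed foci form one undivided group, so the bound is (2 + 4)/15 = 6/15 = 40% (16% to 68%). With a refuted class it is (2 + 3)/15 = 5/15 = 33% (12% to 62%). Among patients with a focus the latter is 5/6 = 83% (36% to 100%).
3. Range. With 2 confirmed of 6 and r refuted, the bound is (6 − r)/15. It runs from 6/15 = 40% at r = 0, where the extra class makes no difference, to 2/15 = 13% at r = 4.
4. Literal biopsy reading. If the refuted focus was refuted by a benign biopsy, it is counted as a true positive and the yield becomes (2 + 1)/15 = 3/15 = 20% instead of 13%.

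**The case against.** The strongest reply is that a negative end state is there already. The heading of Part B names it, Patient Numbers, item b, repeats it, and the natural reading of a two-way rule is that a focus meeting no criterion is not a metastasis. Nothing forbids recording a benign biopsy as physiological, and any clinician would take the biopsy line to mean a positive one. This stands as to intent. It does not supply a criterion, and a default of not confirmed, therefore physiological, would merge benign biopsies with foci never examined.

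A reader might go further and infer that the study can never record a false positive, or that its positive predictive value is 100% by construction. The document supports neither. No predictive value is planned. A figure of 100% arises only if refuted foci are dropped from the denominator, which the protocol does not say.

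It is also fair that limited verification is disclosed, that no restart or termination criterion yet uses the classes, that the work-up will be in the calls and records, and that at most 15 patients can be reviewed one by one. These points limit the harm. Finally, denominators and intervals are commonly left to an analysis plan; but the classification itself is not being deferred, since the protocol sets it and completes only one side.

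**Conclusion.** The point holds as a minor gap in the study's reference standard. The protocol intends a determination that can go either way, but its written criteria for Grade 3 and 4 foci reach only metastasis, the biopsy criterion lacks a result and a site, and refuted foci are not distinguished from unexamined ones in the data awaiting review.

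The confirmed yield, over all foci or all scanned patients, is unaffected provided biopsy is read as positive biopsy. What changes is what can be said about the remainder: in the illustration the upper bound on yield moves from 40% to 33%, and over the range shown by anything from nothing to 27 percentage points (40% − 13%). Those figures rest on assumed counts and one focus per patient; only the 15 is the protocol's. The reading of the criteria needs no assumption.

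**What to change.** For study classification only, with no change to patient care:

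1. State that the biopsy must be positive for DTC at the site matching the sestamibi focus.
2. Give each Grade 3 or 4 focus one of three exclusive classes. *Confirmed*: the existing criteria, with biopsy clarified as above. *Refuted*: benign biopsy, or a benign explanation on imaging, at that site. *Unresolved*: all others at the end of the follow-up the protocol already defines, including negative later imaging and non-matching post-therapy scans. State the status at 12 months, and identify any later diagnosis as such.
3. Report the three counts, the number confirmed over all scanned patients, and the upper bound with unresolved foci counted as confirmed. Give any intervals at patient level, because foci within a patient are not independent.

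A Grade 5 finding would be handled the same way only if the sponsor chooses to extend the rule to it.

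The cost is protocol wording and one column in the data sheet. No procedure, visit or call is added, since the calls already ask which imaging studies and biopsies were ordered. The downside is that many foci may be openly reported as unresolved.

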- b. If Grade 3, 4, or 5 findings are observed, then the study will continue with the follow-up of those patients with those findings to determine as best as reasonably possible whether or not the findings represent metastatic disease from DTC. However, no further patients will be recruited for ^{99m}Tc sestamibi scanning until that data become available and reviewed.
- c. At this time, I am unable to establish what would be criteria to reinstate ^{99m}Tc sestamibi scanning or completely terminate the study.

Statistical analysis:

1. I have initiated a conversation with [name] regarding what additional statistical analysis may be reasonable for such a pilot study.

[figure not shown]
PROJECT ORGANIZATION

Organizational Flowchart

- An authorization chart delegating various functions is being developed.

Project timetable

DATA HANDLING AND RECORD KEEPING

Confidentiality

The Principal Investigator will ensure that subjects' anonymity is maintained. Subjects will not be identified in any reports on this study. All records will be kept confidential to the extent required by federal, state and local law.

Study Documentation and Storage

The Principal Investigator is responsible for maintaining a comprehensive and centralized filing system of all study-related (essential) documentation, suitable for inspection at any time by representatives from the MHRI, IRB, FDA, and/or applicable regulatory authorities.

In addition, all original submission documentation will be maintained and be readily available at InfoEd. All essential documentation should be retained by the institution for the same period of time required for medical records retention. No study document should be destroyed without prior written agreement between the MHRI and the Principal Investigator. Should the investigator wish to assign the study records to another party or move them to another location, MHRI must be notified in writing of the new responsible person and/or the new location.

All data will be coded, and the data and the code document will be on computer in a secure file with password on a secure computer with password.

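### Does the lack of a rule for restarting or ending scanning after the pause call for a change to the protocol?

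*Protocol*

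**What the plan says.** The relevant text is Protocol, Patient Numbers, items a to c.

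- Item a gives the size: "As a pilot study, the present plan is to perform 15 patients". It also gives the one explicit stopping rule, which begins "If no findings of Grade 3, 4, or 5 are identified on the first fifteen" scans; in that case the study is terminated.
- Item b covers the other outcome: "If Grade 3, 4, or 5 findings are observed, then the study will continue with the follow-up of those patients with those findings". Recruitment for scanning is then closed "until that data become available and reviewed".
- Item c says of the step after that review that, for the present, "I am unable to establish what would be criteria to reinstate" scanning or to terminate the study completely.

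The data to be reviewed come from the follow-up described under Interpretation of the sestamibi study, part B. The study team telephones "at 1, 3, 6 and 12 months after the sestamibi scan and/or until diagnosis of the metastatic site" to learn what tests the treating physicians ordered. Of histological confirmation the same part says: "It is anticipated that very few biopsies will be performed". The Statistical analysis section records only that a discussion with a colleague has begun. The Budget table pays for 15 scans.

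**The concern.** A decision rule that is missing when the data arrive can be shaped by those data. Item b keeps further scanning open, item c says no criterion exists, and no visible text requires one before the follow-up results are reviewed or names who decides. With 15 patients, moving the bar by one or two confirmed patients would change the decision often. Judgement also has unusual room here, because few biopsies are expected and confirmation depends on whatever clinical work-up happens to be done.

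A second, smaller doubt is when the pause begins. Item a speaks of the first fifteen scans, while item b is conditional only on findings being observed. Read in isolation, item b could mean a halt as soon as any one scan is graded 3 or higher, in which case the planned 15 scans might not be reached.

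If both doubts were serious, the pilot could be extended or dropped on a criterion chosen afterwards, and its size could be uncertain.

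**Working it through.** **Inputs.** From the protocol: 15 patients (Patient Numbers, a) and 15 budgeted scans (Budget). The protocol gives no finding rate, confirmed yield, alpha, power or precision target, so there is no sample-size figure to reproduce. The rates below are assumptions of 5%, 10% and 20%.

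**1. Plan against budget.** 15 × $295.94 = $4,439.10 and 15 × $10 = $150.00, both as printed. Nothing is budgeted for a sixteenth scan.

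**2. How often the branch without a rule is reached.** The chance of at least one patient with a Grade 3 to 5 finding is 1 − (1 − p)^15.

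| Assumed rate p | (1 − p)^15: item a ends the study | Item b applies |
|---|---|---|
| 5% | 0.463 | 0.537 |
| 10% | 0.206 | 0.794 |
| 20% | 0.035 | 0.965 |

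So at rates of 5% and above, the undefined branch is the more likely outcome.

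**3. How much a threshold would matter.** Suppose scanning restarted when at least r patients were confirmed, with confirmed yield q per scanned patient. Then P(X ≥ r) = 1 − Σ C(15,k) q^k (1 − q)^(15−k), summed over k = 0 to r − 1. At q = 10%, P(0) = 0.9^15 = 0.206, P(1) = 15 × 0.1 × 0.9^14 = 0.343 and P(2) = 105 × 0.01 × 0.9^13 = 0.267. The chances of restarting are therefore 0.794, 0.451 and 0.184 for r = 1, 2 and 3.

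| Assumed yield q | r = 1 | r = 2 | r = 3 |
|---|---|---|---|
| 5% | 0.537 | 0.171 | 0.036 |
| 10% | 0.794 | 0.451 | 0.184 |
| 20% | 0.965 | 0.833 | 0.602 |

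The arithmetic is right, but neither the cut-offs nor the yields come from the protocol. Any binomial count with n = 15 behaves this way. The table shows that a choice would matter if one were made; it does not measure a defect in this plan.

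**4. What the pilot can report.** With 15 scans the natural result is a proportion with an exact 95% interval: 0/15 gives 0% to 21.8%, 1/15 gives 0.2% to 31.9%, 3/15 gives 4.3% to 48.1%, and 5/15 gives 11.8% to 61.6%. None of these depends on what is later decided about further scanning.

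**5. When the pause begins.** Item a sets its condition on the first fifteen scans, and item b follows as its counterpart for the opposite outcome. A halt as soon as any one scan is graded 3 or higher would contradict item a, which says that "the present plan is to perform 15 patients". Read together, the items put the pause after scan fifteen, so the number of scans is not in real doubt.

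**6. When a rule could still be written in advance.** The calls start at month 1, the study team makes them, and nothing blinds it. A criterion untouched by follow-up results would have to precede the first month-1 call to a patient with a finding. Waiting towards month 12 would be too late.

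**The case for a change.** The strongest case for a change is that the gap is in the protocol's own words and is cheap to close. The protocol itself keeps further scanning open, ties it to a data review and says it has no rule, so an unseen analysis plan is not a full answer. The branch is likely to be reached, confirmation is soft, and there is no monitoring board to take the decision. One sentence closing the pilot at 15 would use the same scans and the same follow-up.

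Much of this stands as description. There is no criterion, and no visible text demands one before the review. What does not stand is the harm. Deciding from pilot results whether to scan more patients is an ordinary use of a pilot, and with no test or claim of success there is no error rate to inflate. While no decision is made, recruitment stays shut. Closing at 15 would therefore alter only the right to extend within the same protocol. The alternative, a fixed number of confirmed patients, has its own cost: with few biopsies, confirmed yield may understate true yield, and a rigid cut-off could end work on a useful scan.

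**Conclusion.** The observation is correct but no change is needed. Item c is a disclosed deferral, and the protocol's default in the meantime is to stop. The plan and budget cover exactly 15 scans, and the descriptive result from them is the same whether or not a restart rule exists. The size of the issue is limited to an optional later decision. The threshold probabilities (79%, 45% and 18% at an assumed 10% yield) are illustrations only, since the protocol supplies neither yields nor cut-offs.

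The conclusion rests on three things: the pause falls after the fifteenth scan, which is the natural reading of items a and b together; the 15-patient result is reported descriptively; and any extension is recognised as decided after the pilot results were seen. If the sponsor later wanted a confirmatory claim from pooled pilot and extension data, the missing rule would matter, but nothing in this protocol proposes that.
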